5.4 Adherence Assessment

The total number of treatments will be decided by the treating clinician based on each individual participant’s clinical presentation and response to care, as is done in clinical practice. We anticipate 4-6 visits being prescribed for most participants receiving SMT, 4-8 visits for most participants receiving SSM, and 2-4 visits for most participants receiving medical care. Participant adherence to assigned interventions will be documented at each visit in the clinical notes.

Treatment adherence has been defined in the Threshold Criteria for Transition as attending $\geq 75\%$ of prescribed intervention visits. We have expanded on this definition by including a minimum number of visits for each intervention and requiring participants not drop out of active care to be considered adherent. A minimum of 2 sessions will be required for participants in SMT and MC, and minimum of 4 for the two groups receiving SSM, but additional sessions may be needed.

Intervention fidelity will be assessed by review of treatment visit activities that address required, allowed and prohibited interventions. In addition, fidelity will be assessed by video/audio recordings or in person observations of randomly determined intervention visits. Fidelity assessments will occur monthly, for six months, on each provider currently treating patients, then quarterly thereafter. If concerns arise during quarterly reviews, the provider may resort back to monthly fidelity checks as needed. The DCC will monitor the treatment administered forms for activities defined as ‘out of scope’ for the defined intervention (e.g., spinal manipulation delivered to a participant assigned to structured self-management). Out of scope activities indicating potential crossover will be flagged through automated real-time alerts created by the DCC which will immediately be sent to the relevant site’s PI and study coordinators. The site study coordinators are best suited for contacting providers, as they will be familiar to them and will have developed collaborative working relationships that ensure successful project implementation. Additional actions would include remedial training for the providers and potential removal from providing study care.

5.5 Rescue Medication

Participants not assigned to MC who experience a significant worsening of LBP symptoms that cannot be managed by the assigned and concomitant interventions will be referred to a study medical care provider for a short-course of rescue medications. Skeletal muscle relaxants and non-steroidal anti-inflammatories are the first line rescue medications that will be offered based on the participant’s individual medication risk profile. Additional medication may be used when first line rescue medications are contraindicated or do not sufficiently manage the participant’s pain (e.g., opioids, benzodiazepines, antiseizure medications).⁴⁶ Use of rescue medication will be monitored and differences across intervention arms will

be compared. Further, medical providers should make reference to the Back in Action booklet and reinforce its content (e.g., the favorable prognosis for acute/subacute back pain and the importance of staying active).

6. STUDY PROCEDURES

6.1 Schedule of Evaluations

See Table on next page

Assessment	Initial Screen	Baseline/ Enrollment (Day 0)	Intervention Visits (Months 0-2)	Weekly Follow-Up (Weeks 1-52)	Follow-Up (Week 2)	Monthly Follow-Up (Months 1-12)	Follow-Up (Month 1)	Follow-Up (Month 2)	Follow-Up (Month 6)	Follow-Up (Month 12)
Informed Consent	x	x								
Demographics	x	x								
Medical History & Current Medications		x								
Physical Exam including objective outcomes		x						x		
Inclusion/Exclusion	x	x								
Technology Assessment**		x								
COVID -19 Impact		x						x	x	x
TUQ**		x					x	x		
STarT Back Screening Tool Status	x							x	x	x
Chronic LBP status (NIH RTF definition)	x	x							x	x
Chronic interference with daily activities	x	x							x	x
LBP intensity	x	x		x						
LBP frequency		x		x						
Pain Trajectory		x								x
Implementation Measures	x	x						x	x	x
Randomization/Enrollment		x								
Treatment Administered (booster sessions allowable in months 3-12)			x							

Intervention Uptake							x	x	x	x
Disability, PROMIS, healthcare and medication use, and productivity loss		x				x				
Adverse events*		x	x			x				
Satisfaction and global improvement								x	x	x
Non-specific factors (HEAL)		x			x		x	x	x	x
Psychosocial Mediators (self-efficacy, coping, kinesiophobia, and pain catastrophizing)		x						x	x	x
Participant Close Out										x

*Participants can also report adverse events to the PI's or study staff at any point during the trial
 ** Technology Assessment and the Telehealth Usability Questionnaire (TUQ) will be administered to participants who are enrolled in the 2-arm study only. Technology Assessment and the Telehealth Usability Questionnaire (TUQ) may be administered to participants in the 4-arm study if applicable (e.g., if screening and/or treatments are done virtually).

6.2 Description of Evaluations

6.2.1 Screening Evaluation

The following evaluations will occur to determine if the candidate is eligible for the study.

Consenting Procedure

- Potential participants will consent at 3 different time points: the initial screen online, phone screen, and at an in-person or videoconference baseline screening appointment.

Initial screening

- Potential participants will read a brief online description of the study, including the purpose, study design and procedures to help them decide if they want to complete the initial screen. Consent is provided by checking a box that will allow them to proceed with the initial screening.
- Phone Screening

Baseline Screening Appointment

- Potential participants will be given a copy of the consent form to review on their own that will describe the screening and study procedures. See Section 11.2 for a full description of the consent form. They will be given ample time to review the form on their own and ask questions.
- The Principal Investigators, or designee (i.e., research staff) will review the consent form, section by section, one-on-one with each potential participant; participants will be invited to ask questions as they proceed through each section.
- Informational materials (e.g., flow chart or PowerPoint) will be used to facilitate understanding.
- All participants will be given information related to the COVID-19 pandemic and potential risks associated with research participation
- A signed and dated consent form will be obtained from each study candidate and research staff conducting the consent process will sign as a witness. All participants will be given a copy of the signed consent form for their personal records. Participants will provide electronic consent (e-Consent in REDCap) or written consent.
- Original signed consent forms will be secured in the respective participants' research file at each of the respective clinical coordinating centers or in REDCap. Scanned consent forms will be sent electronically to the DCC for monitoring.
- Only individuals who demonstrate comprehension will be considered eligible to participate. Persons who are not able to read and write in English or consent for themselves are ineligible.

Training

All research staff obtaining informed consent are required to undergo project specific human subjects training that addresses the essential components to the informed consent process. See Section 11.2 for

additional information about the consent form. In addition, staff will complete human subjects training in accordance with the IRB of record and/or the staff member's institutional human subject training requirements.

Changes to the Informed Consent Form

In the event the informed consent form changes, following necessary IRB approvals, study staff will meet with the PI or designee and review changes to the form prior to conducting consent with a potential participant. See the Participants and Confidentiality section for additional information.

If potential participants need to be informed of specific changes in the risks or benefits of study participation, an addendum consent will be used. This addendum will be used to inform enrolled participants about significant new findings that may have a bearing on their willingness to continue participation in the study. The addendum consent will be given to the participant at a study visit or mailed to the participant's home.

Screening

Screening will occur at 2 time points: an initial screen (online and phone) and a face to face (e.g., in-person or videoconference) baseline screening appointment.

Initial Screening (Online/Phone)

- Following consent, potential participants will be asked a series of self-report questions to screen basic eligibility. Persons who meet basic inclusion criteria (e.g., age, medium or high risk on STarT Back Screening Tool, LBP intensity of 3 or higher, English literacy) and who otherwise have no obvious exclusions (e.g., pregnancy, history of surgical fusion of lumbar spine) will be contacted by study staff, who will ask specific health-related, questions pertaining to inclusion (e.g., LBP episode duration).
- In-person or videoconference screening appointments will occur as soon as possible, but must occur within 30 days of completing the phone screen; otherwise, the initial phone screen will be redone.

Baseline Screening (In Person/Videoconference)

- Written or e-informed consent will be collected from participants prior to any screening procedures at this visit.
- Participants will complete self-report questionnaires to determine eligibility that include:
 - Demographics
 - Current back pain intensity and duration
 - Diagnosis of serious mental health disorders and related treatment; if major depression is suspected or reported by the participant, the Patient Questionnaire-2 (PHQ-2)¹²⁶ will be administered; a score of greater than or equal to 3 will lead to additional screening for suicidality. Suicidal ideation will be collected using question 12 from the Quick

Inventory of Depressive Symptomatology-Self Report (QIDS-SR)¹²⁷ and a score of greater than or equal to 2 warrants exclusion and referral.

- Substance abuse. All participants who indicate they drink alcohol will be asked if they drank more alcohol than intended in the previous 6 months. If affirmative, additional questions will be asked related to how often they have drunk 6 or more drinks on one occasion. Those who indicate having done so at least weekly will receive additional screening: the 10-item Alcohol Use Disorders Identification Test (AUDIT) for alcohol.¹²⁸ Scores of greater than or equal to 20 on the AUDIT is exclusionary and warrants referral. AUDIT will be available to administer at any time if the clinician suspects a problem. Participants reporting the use of illegal drugs or prescription medication for nonmedical reasons in the last year will complete the 10-item Drug Abuse Screening Test (DAST)¹²⁹⁻¹³¹ for drugs. Scores of greater than or equal to 6 on the DAST is exclusionary and warrants referral. The DAST will be available to administer at any time if the clinician suspects a problem.
- Comorbidities
- A licensed healthcare provider (e.g., DC, PT, MD, advanced practice provider) will conduct a medical history and a focused low back physical exam that will include posture assessment, orthopaedic and neurological tests, palpation (in-person only) etc. Current medications and vitals (in-person only) will be collected. Participants undergoing screening assessment via videoconference will be asked additional screening questions regarding potential hypertension as remote assessment of blood pressure is not planned. Suspicion of declining cognitive function during clinical exam will lead to administration of the Mini-mental state examination. A score of 23 or below is exclusionary.¹³²
- Women of childbearing age require a pregnancy test. Women who have had a hysterectomy or are postmenopausal will not require a pregnancy test. Persons who are in same sex relationships, transgender and/or transitioning, celibate, LBTGQ+, can refuse a pregnancy test and still be eligible to participate. For remote videoconference baseline appointments, participants will be mailed a pregnancy test and instructed to take the test during the baseline appointment and show research staff the result.
- Potential participants who present with signs and symptoms suggestive of a specific cause of LBP (e.g., nephrolithiasis, infection, fracture), contraindication to SMT or SSM (e.g., inflammatory arthropathies of the lower back), or other condition that warrants medical attention will be referred to their medical provider for follow-up and management.

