4.2 Exclusion Criteria

Candidates meeting any of the following exclusion criteria at baseline will not be enrolled:

- Average LBP characterized as severe in the month preceding the current episode/aggravation
- Specific non-mechanical causes of LBP (e.g., infection, cancer)
- Contraindications to SMT or SSM (e.g., spinal fracture, progressive neurological deficits, inflammatory arthropathies of the lower back, surgical fusion of lumbar spine)
- Active management of current episode of LBP by another healthcare provider. Participants must stop management with their current provider to enroll in the study (e.g., SMT, PT, prescription medication, CBT, a structured program led by a healthcare provider that may include pain education, mind-body practices, coping strategies etc).
 - Participants taking prescription opioid medication for LBP are required to obtain a note from a prescribing/medical provider to confirm they have safely discontinued their opioid medication.
- Serious comorbid health condition that either requires medical attention (e.g., severe hypertension, inadequately managed serious mental health conditions, substance abuse), or has a risk for general health decline over the next year (e.g., Parkinson's disease, Multiple Sclerosis, organ failure, Dementia, Alzheimer's disease).
- Pregnancy, current or planned, and nursing mothers during the study period.
- Inability or unwillingness to give written informed consent.

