5.1.4 Medical care

Medical care is informed by the American College of Physicians guidelines on noninvasive treatment for LBP⁴⁶ and reflect what is delivered in primary care clinics. Medical care will be provided by licensed medical providers (e.g., MD, APN, PA) with a minimum of 3 years managing musculoskeletal pain patients. Decisions regarding medical care (e.g., pharmacological management) and visit frequency during the initial 8-week intervention period will be made collaboratively by the provider and patient, as normally occurs in clinical practice. Care will be provided via HIPAA compliant video conference (e.g., Zoom), within outpatient clinics affiliated with UPITT and UMN, and/or over the phone: the Physical Therapy Clinical and Translational Research Center, Homewood Community Engagement Center Wellness Pavilion and the Berman Center for Outcomes and Clinical Research, respectively. In case of a recurrence of an acute LBP episode during the 10 month follow-up period participants have the option to continue to receive medical care; this treatment will occur in the study clinics with the same provider if possible. They will not be offered the option to receive treatment delivered in any of the other 3 study groups during this follow-up period.

Medication Delivery: Medication will be prescribed topically and/or orally, in tablet form. Participants can purchase over-the-counter (OTC) medications (e.g., Ibuprofen, 4% lidocaine patches); however, these will be paid for by the study. Prescription medications (see Required and Allowed Interventions) will be sent to the patient’s preferred pharmacy by the provider or research staff.

- The first visit will occur in the clinic or via virtual HIPAA compliant videoconference (Zoom). Clinicians will review information collected during the screening phase, and conduct their own medical history and exam as needed. A treatment plan will be established, and the provider will follow-up with the participant (in-person, via videoconference or by phone) within 7 business days of the initial visit.

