- The second and subsequent encounters between the provider and participant may occur in the clinic, virtually using HIPAA compliant Zoom, or over the phone. During this encounter the provider will get a sense of how the patient is responding to the treatment. Medication adjustments, including class, dose, and frequency can be made based on the participant's current presentation and response. As described above, the need for subsequent in-person, videoconference visits, and/or phone calls will be made collaboratively between the provider and participant.

Side-Effects¹²⁵: Pharmacological therapies are associated with increased AEs compared to placebo.⁷ Several protections are in place to minimize risks, including reminding participants to take their medication as prescribed and to contact the study clinician if there are changes to their medication regimens to avoid drug-drug adverse interactions. Also, clinicians will assess the potential for risk factors based on the patient's medical history prior to prescribing/recommending (prescription and OTC) medications and will suggest the lowest effective dose(s) for the shortest time necessary.

- Allergic reaction
- Cardiovascular symptoms: hypotension, edema, flushing,
- Central nervous system: dizziness, weakness, ataxia, fatigue, drowsiness, headache, stimulation, insomnia, sedation, tremor, syncope
- Chemical dependence
- Dermatologic: itchy skin, rash, sweating
- Endocrine & Metabolic: weight gain
- Gastrointestinal symptoms: nausea, vomiting, dry mouth, abdominal pain, dyspepsia, diarrhea, GERD, constipation, bleeding
- Kidney failure (excessive NSAIDs use)
- Liver failure (excessive Acetaminophen use)
- Ophthalmic: visual field loss, blurred vision
- Respiratory: depression, arrest, apnea

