6.2.2 Enrollment, Baseline, and/or Randomization

Enrollment

Enrollment is defined as the date of randomization at which point all eligibility criteria are confirmed and the individual has agreed to participate; this is recorded on a case-report form. AEs will be collected after the participant is enrolled. Participants will be told to contact study staff and/or providers about any health related changes they experience. See Safety Assessments and the DSMP for additional details.

Baseline Assessments

For participants who have successfully been screened for eligibility and are enrolled into the study, baseline assessments are performed against which to measure the study outcome. These will also ensure the groups are balanced with respect to baseline characteristics.

Primary and secondary outcomes will be measured using web-based, self-report questionnaires administered free of provider and investigator influence.

Baseline characteristics

Important baseline characteristics (e.g., demographics, past healthcare use, COVID-19 impact¹⁹⁰, LBP duration, prior episodes of LBP, visual trajectory questionnaire for pain¹⁸⁶, Quebec Task Force classification of spinal disorders¹³³) will be collected through web-based, self-report questionnaires and the screening provider's medical history and physical exam. Baseline measures included in the NIH research task force's minimum dataset will be collected.⁷³

Primary Outcome Measures

The following primary outcome measures will be collected during the baseline assessment.

- Low back pain impact is defined as a combination of pain intensity, pain interference with normal activities, and functional status, using 9 items of the 29-item PROMIS short form. These items have substantial research support to validate their discriminatory and prognostic importance. Scores on the 9 PROMIS-based items yielding Impact Stratification range from 8 (least impact) to 50 (greatest impact).¹⁹¹
- LBP Intensity: participants will be asked to rate their average LBP over the last week on an ordinal 11-box NRS (0=no LBP, 10=the worst LBP possible). Several studies have shown that ordinal pain scale measures perform as well as the 10-cm Visual Analog Scale (VAS),¹³⁴ a simple, frequently used valid assessment of variation in pain intensity^{119 135} and a reliable measure of treatment efficacy.¹³⁶ The advantage of the 11-box scale over the VAS is that it is easier to administer and score.¹¹⁹

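### Some of the categories that allow refusal of the baseline pregnancy test do not determine whether pregnancy is possible; for those who refuse, the exclusion rests on self-report and history (minor safety point)

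*Combined protocol and SAP*

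**What the plan says.** Section 4.2 lists as an exclusion, without qualification: "Pregnancy, current or planned, and nursing mothers during the study period".

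Section 6.2.1 (baseline screening) requires a test in women of childbearing age. For remote visits a kit is mailed, and the participant shows the result to staff. Two exceptions follow. The first is physiological: "Women who have had a hysterectomy or are postmenopausal will not require a pregnancy test". The second is a right to refuse: "Persons who are in same sex relationships, transgender and/or transitioning, celibate, LBTGQ+, can refuse a pregnancy test and still be eligible to participate". No further condition is attached to that right.

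The other checks that bear on pregnancy at entry or before a drug is given are:

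- The online and phone screen in Section 6.2.1 works by self-report and names pregnancy as an example of an obvious exclusion.
- At the baseline visit, "A licensed healthcare provider (e.g., DC, PT, MD, advanced practice provider) will conduct a medical history and a focused low back physical exam".
- Section 6.2.2 states: "Enrollment is defined as the date of randomization at which point all eligibility criteria are confirmed and the individual has agreed to participate".
- In MC (Section 5.1.4), "Clinicians will review information collected during the screening phase, and conduct their own medical history and exam as needed". Clinicians also assess risk factors from the patient's "medical history prior to prescribing/recommending (prescription and OTC) medications". Section 7.2 repeats this.
- Sections 5.2.3 and 5.5 ask that the choice of drug reflect the individual's medication risk profile.

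**The concern.** The two exceptions rest on different grounds. The first covers people who cannot be pregnant. The second mixes one ground that bears directly on the question (celibacy), one that bears on it roughly (a current same-sex relationship), and two that do not determine it (being transgender or in transition, and LBTGQ+ identity). On the literal wording, a bisexual woman with a male partner or a transgender man with a uterus may refuse, while a heterosexual woman with the same exposure may not. The same risk is handled differently according to identity.

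At stake is an unrecognized pregnancy at baseline followed by study medication. Section 5.2.3 makes NSAIDs or skeletal muscle relaxants first-line in MC. It permits opioids, benzodiazepines and antiseizure drugs, among others, when first-line drugs fail or are not tolerated. Section 5.5 makes the same first-line classes available as rescue in the other arms, so the exposure is not confined to MC.

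**Working it through.** No arithmetic applies. The check sets the sections side by side.

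1. **Does the exclusion still apply to someone who refuses?** Yes. Section 4.2 has no carve-out, and Section 6.2.2 requires every criterion to be confirmed at randomization. Section 6.2.1 waives the test, not the criterion.

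2. **Does each category settle whether pregnancy is possible?**
   - Hysterectomy, postmenopausal: yes.
   - Celibate: directly relevant, but self-declared and with no time window.
   - Same-sex relationship: lowers the chance but does not settle it.
   - Transgender or in transition: does not settle it.
   - LBTGQ+: does not settle it.

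3. **What can the remaining checks find in someone who refuses?**
   - The initial screen asks the person, so it finds a pregnancy the person knows about.
   - The baseline visit takes a history and a focused back examination. No pregnancy-specific step is listed apart from the test.
   - Confirmation at randomization covers pregnancy by reference and gives no method of its own.
   - The MC clinician's review of screening information, and the risk assessment before prescribing, draw on the record and the history.
   - The rescue prescriber considers the individual's medication risk profile.

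   All of these can find a known pregnancy. None describes a step that would find an unrecognized one.

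4. **Is there a later test?** The schedule in Section 6.1 lists no separate pregnancy test and no repeat. Section 5 allows further treatment if pain recurs, so a pregnancy that begins after baseline depends on history-based checks in tested participants too. The point therefore concerns only pregnancies present at baseline.

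5. **Can refusal distort the comparison of arms?** No. It happens during screening, before randomization, and cannot depend on the assigned arm.

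6. **How many people are affected?** The documents do not say how many participants fall in the listed categories or how many refused. The version 8 revision log (June 2023) records an update to the pregnancy test requirements. If the right to refuse began then, it covers only later enrollees. The documents give no basis for a rate or a count.

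**The case against.** The strongest case against the point is that little is left uncovered. Section 4.2 also excludes planned pregnancy and nursing, which no test can show, so applying the criterion already means asking every candidate. The rule is a permission and not an automatic waiver, so people in these categories may still be tested. It looks deliberate, and Section 11.1 sends protocol modifications to the IRB. Clinicians must assess risk before prescribing. The case report forms, manual of operations, safety monitoring plan and consent form were not available, and any of them may hold a further question or pass test status to the prescriber.

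Most of this stands. It reduces the point to an unrecognized pregnancy in someone who refuses, and it means that silence about recording refusals, or about what the rescue prescriber sees, is not shown to be a gap. It does not remove that residue. Asking cannot find what the person does not know, and the protocol evidently thought a test worth requiring of everyone else of childbearing age.

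A fair warning also applies to the remedy. An open-ended attestation that pregnancy is not possible could let more people skip the test than now, for example those relying on contraception. The list has to be closed.

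A reader might infer more than the documents support. That pregnant people in these categories may enroll is wrong, because the exclusion applies to them unchanged. That nothing screens them is also wrong, because several self-report and history checks remain. That the treatment comparison is compromised does not follow, because refusal precedes randomization.

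**Conclusion.** The point holds as a minor matter of participant safety and consistent application of eligibility. The right to refuse rests partly on categories that do not determine whether pregnancy is possible. For those who use it, the exclusion depends on self-report and history, which cannot detect an unrecognized pregnancy before MC or rescue drugs are given.

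Harm would require a person to be in a listed category, to refuse, to have an unrecognized pregnancy at baseline, and then to receive study medication. Section 5.3 says rescue was rarely needed in the investigators' earlier studies, which narrows the route outside MC. The number is probably very small, and no figure should be attached to it.

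The conclusion assumes that the protocol text is the operative rule and that no unseen document adds a condition to refusal. If recruitment has closed, the benefit for this trial is limited.

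**What to change.** In Section 6.2.1, replace the list of categories with a closed criterion, for example:

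*A person of childbearing age may decline the test and remain eligible only if they attest to one of the following: no uterus; postmenopausal; or no sexual activity that could lead to pregnancy since the last menstrual period (or within a stated window). Use of contraception or a partner's sterilization does not qualify. Otherwise the test is required, whatever the person's identity or relationship.*

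This extends the ground already used for hysterectomy and menopause. It keeps the accommodation for people to whom the test is irrelevant, and nobody has to disclose identity or orientation to use it. An attestation is still self-report; the gain is that anyone who cannot make it takes the test.

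The cost is one sentence of protocol text and one extra baseline question. A few people who may refuse now but could not attest would have to test or be excluded. Nothing in the statistical plan changes.
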